8.1.12 Anthropometrics

Anthropometrics will consist of weight, height, and BMI as determined from the most recent data available in the electronic health record. Data recorded >1 year prior to study enrollment will not be used.

8.1.13 Medications

Medications will be obtained from the electronic health record. Specific medications recorded will be:

- 8.1.13.2 Warfarin
- 8.1.13.3 Novel oral anticoagulants
- 8.1.13.4 Medications for blood pressure
- 8.1.13.5 Medications for cardiovascular disease, e.g. beta blockers, ACE inhibitors, ARBs, dihyropyridine and non-dihydropyridine calcium channel blockers.
 - 8.1.13.6 Other antiplatelet agents, e.g. clopidogrel, prasugrel, ticagrelor
 - 8.1.13.7 Medications for diabetes (insulins and oral agents)

8.1.14 Medical History

Medical history will be obtained from EHR problem lists and include:

- 8.1.14.2 Congestive heart failure
- 8.1.14.3 Hypertension
- 8.1.14.4 Diabetes
- 8.1.14.5 History of stroke or TIA
- 8.1.14.6 Vascular disease, as determined by history of myocardial infarction as a clinical event; coronary angiography with stenosis documented as >50%; peripheral arterial disease, as documented by symptomatic claudication, ankle-brachial index documented as ≤0.90, carotid stenosis >80%, or abdominal aortic aneurysm measured at ultrasound by >5 cm.
- 8.1.14.7 Cardioversion procedures, including electrical cardioversion, pharmacologic cardioversion, and pulmonary vein isolation (AF ablation)

8.1.15 Health Care Utilization

Information on health services utilization, including hospitalizations, outpatient visits, and other specialty referrals, and medication usage by abstracting patients' medical records. We will also advise patients to report any hospitalizations or other medical events (especially those that occur at non-UPMC locations) to our research team by telephone any time. All reports of utilization will be investigated using hospital records.

9 Follow-up Visit Schedule

Throughout the duration of baseline to 4 months

All participants will receive scheduled check-in calls at study day 7, 14, 30, 60 and 90. These calls will serve to support participants and attend to any difficulties they may be experiencing with the study protocol and/or device(s) they are asked to use daily. Participants who haven't mailed back their medical release forms will be reminded to do so during these calls.

Study staff will maintain relational agent and Kardia results daily on a web-based dashboard developed by our collaborators at Northeastern University with the help of the Epidemiology Data Center (EDC). Agent dashboard results will consist of use statistics, reported symptoms, and self-

reported adherence to anticoagulation. Kardia results include date and time of use and heart rate and rhythm. Dashboard results will be reviewed daily.

2nd Study follow-up: - +~4 months

Participants will complete the 2nd visit at 4 months in person or over the phone if the participant is unable to meet with study staff. Study staff will send reminder cards/e-cards to the participants prior to their follow-up visit. Participants will complete a feedback survey as well as assessments and questionnaires identical to several of those done at the baseline visit. Medical records will be reviewed to assess health care utilization (emergency visit, hospitalization, and number of days hospitalized). Study iPhones will be returned during the 4-month visit, either in person or mailed back to the study team in a postage prepaid box provided to the participant. This visit will take participants 45-60 minutes to complete.

3rd Study follow-up: - +~8 months

The 3rd follow up will be conducted over the phone by trained interviewers.

Medical records will be reviewed to assess health care utilization (emergency visit, hospitalization, and number of days hospitalized). Participants will complete assessments and questionnaires identical to several of those done at the baseline and month 4 visits.

4th Study follow-up: - +~12 months

The 4th follow up will be conducted over the phone by trained interviewers. Participants will complete assessments and questionnaires identical to several of those done at the baseline and month 4 and 8 visits. Medical records will be reviewed to assess health care utilization (emergency visit, hospitalization, and number of days hospitalized).

At time- +~12 months

Medication fill data, for purposes of calculating the proportion of days covered (PDC), a common measure of medication adherence, will also be extracted from the EHR and from the pharmacist(s). Study staff will assess the EHR for incidence of adverse cardiovascular event and mortality. Study staff will also use the National Death Index to identify participant deaths and their dates.

10 Clinical Trial Oversight and Monitoring

10.1 Data Safety Monitoring

This study will recruit subjects at the University of Pittsburgh Medical Center (UPMC) who have a chronic heart rhythm disease, atrial fibrillation (AF), and are receiving anticoagulation for stroke prevention. Participants are expected to constitute a high-risk population, as they will live in rural settings, have limited socioeconomic resources, and likely have low health literacy. The study will consist of 264 adults who will be randomized to an intervention or control cohort. The intervention cohort will receive (1) a smartphone with a relational agent application, described in the application as an embodied conversational agent, and (2) the AliveCor Kardia heart rate and rhythm monitor (described here as Kardia for simplicity). Topics and content provided by the relational agent will focus on selfcare in AF, including symptom monitoring, maintenance, and health-promoting behaviors. The relational agent will also provide education about AF and its treatments and outcomes, and health-related quality of life. The Kardia is an FDA-approved device that also uses the smartphone. It provides 30 continuous seconds of ECG monitoring similar to a Lead I rhythm strip of a 12-lead ECG. Both devices are non-invasive and may be described as smartphone applications, or apps. Participants randomized to the control arm will receive an educational session about AF and a smartphone with the WebMD application installed. participants will use the intervention for 4 months and have return visits at 4-, 8- and 12-months with assessments as documented in the application. Intervention participants will use the smartphone in order to have interactive exchanges with the relational agent and to check their heart rates and rhythm with the Kardia. The study team will follow up on the results of the smartphone agent and the Kardia, as these mobile health applications can provide important information that can be used to guide and enhance patient care. If results meet specified criteria, then the study team will send alerts through the electronic health record to the physicians and care teams that provide care for intervention participants. The research questions being investigated by this study consequently have direct implications for clinical care and patient management.

10.2 Data Safety Monitoring Board

To ensure the safety of the participants and the validity and integrity of the data, the clinical trial will have a Data and Safety Monitoring Board (DSMB). The DSMB will be charged with evaluating the quality of trial administration, monitoring safety issues, and providing guidance on scientific, methodological and ethical issues. As its first priority, the DSMB will approve and codify the DSMB charter. Following approval by the DSMB, the charter will be submitted to the NHLBI for review and approval. The DSMB charter will describe the study protocol, data and safety monitoring plan, operation and format of DSMB meetings, Adverse Event (**AE**) definitions, AE reporting templates and case report forms, stopping rules for the trial, and a schedule for conducting blinded assessments of study benefit and safety.

The DSMB will be valuable for ensuring the quality and scientific validity of the study. It will be comprised of 3 individuals. Members will adhere to the University of Pittsburgh's policy on conflict of interest and are expected to participate for the duration of this clinical trial. The DSMB will have scheduled meetings every 6 months to evaluate and review safety, review any potential breaches in protocol, and discuss summaries of the interim AE and serious adverse event (**SAE**). The DSMB will make recommendations concerning (1) participant safety, (2) the benefit and risk ratio of the study, (3) the efficacy of the study intervention, (4) any possible amendments to the study protocol or consent, and (5) proposed ancillary studies and their impact on participant burden. Following each meeting, the DSMB will make recommendations on continuation, modification, or

termination of this trial. The DSMB will further evaluate adherence to the protocol and the recruitment and retention of participants. DSMB meeting format will be open or closed session, as determined by DSMB Chair with regard to NHLBI participation. Additional meetings will be arranged as per the charter for the need to review events or issues arise (such as an unexpected number or severity of AE). For safety monitoring, discussion will take place on whether or not any reported incident is unanticipated and/or places subjects or others at greater risk of harm, and if protocols or consent processes need to be modified. The DSMB will review the annual progress report on (1) confirmation of adherence to the data and safety monitoring plan, (2) a summary of data and safety monitoring issues for the since the last report, (3) changes in the research protocol or data and safety monitoring plan, and (4) IRB status and approvals.

10.3 Adverse events

Individuals enrolled in this trial will have a chronic disease, atrial fibrillation. This trial will use standard definitions for adverse events that accord with Federal mandates for human subjects' protection and adverse event reporting.

Identification of AE, SAE, and unanticipated problems. The study team will learn of AE, SAE, and unanticipated problems by participant interview at the 4-, 8- and 12-month assessments; direct contact by participants during the scheduled check-in calls; review of the electronic health record; communication from referring physicians or participants' providers; or contact with the study team initiated by family or other participant surrogates.

Responding to AE, SAE, and unanticipated problems. Study staff will follow guidelines set forth by the University of Pittsburgh's Institutional Review Board (IRB) and the Human Research Protection Office. The University of Pittsburgh Epidemiology Data Center, serving as the Data Coordinating Center (EDC) for the trial, will develop AE case report forms specific to this trial. The project manager and PI will prospectively record all incidents that meet any of the above definitions, and then classify AE within 24 hours of identification using the following criteria:

- 1. Severity (mild, moderate, severe, life threatening);
- 2. Relationship to study intervention (not related, unlikely, possibly, probably, or definitely related);
- 3. Action take regarding study intervention (none, medical intervention, hospitalization, intervention discontinued, or other);
- 4. Outcome of AE (resolved, recovered with minor sequelae, recovered with major sequelae, ongoing or continuing treatment, condition worsening, death, or unknown);
- 5. Expected AE (yes or no); and
- 6. Whether the AE constitutes an SAE.

All AEs and classification according to these criteria will be maintained in a log and signed by the PI. In accordance with the University of Pittsburgh IRB, all internal AEs which are (1) unexpected, fatal or life-threatening, and (2) related or possibly related to the relational agent /Kardia intervention will be reported to the IRB within 24 hours of learning of the event.

For this clinical trial, an example of an AE that would merit classification as an SAE would be hospitalization. AEs that are classified as SAEs will be further reviewed to determine if (1) they are unexpected, and (2) related or possibly related to the study procedure (relational agent relational agent and AliveCor). SAEs meeting these criteria will be reported to the IRB within 2 business days (48 hours) of learning of the event. In accordance with NHLBI regulations, SAEs

will be reported within 7 days of initial receipt of information to the NHLBI. SAE that are non-fatal and non-life-threatening will be reported to the NHLBI within 15 days of the receipt of information.

The project manager, co-investigators, PI and statistician will review aggregate data on AEs and SAEs regularly. The DSMB will be notified simultaneously with the IRB and NHLBI and will receive case report forms and documentation with a request for timely response to the SAE.

Unanticipated problems will likewise be reported to the IRB within 24 hours of the PI learning of the incident if they are fatal or life-threatening. The report will explain why the incident is considered an unanticipated problem and how the protocol will be modified. Incidents that do not meet the three criteria for unanticipated problems (unexpected, given the research procedures; related or possibly related to participation in the research; and suggest that the research places participants at a greater risk of harm than previously known or recognized) will be considered as either potential AE or classified as SAE as defined above. Unanticipated problems that are not SAEs will be reported to the IRB and the NHLBI within 14 days of the PI becoming aware of the problem.

Risk assessment. Participation in the proposed research may be considered moderate risk. This is because (1) the investigation may have direct implications for clinical care; (2) findings identified by use of the relational agent and Kardia may enter the electronic health record and thereby result in modified care; and (3) recruitment of high-risk populations (i.e., individuals with limited socioeconomic resources, low health literacy, and/or racial/ethnic minorities). As stated in the Informed Consent, use of the relational agent does not replace routine, urgent, or emergent clinical care. Participants in this trial will be instructed NOT to delay seeking care because they are using the relational agent to address a medical problem, question, concern or issue. All AE will be closely evaluated in order to ascertain if the AE is related or possibly related to participation in this research. Participant use of the relational agent and Kardia in proximity to the AE will be scrutinized for whether or not use of the intervention delays participants from seeking care. If necessary, participants will be directly interviewed to appreciate their understanding of the relation of their participation in this research and the occurrence of the AE. The project manager, coinvestigators, and PI will review the AE and evaluate for their association with the intervention. The results of such examination will be recorded on a unique report form as prepared by the Epidemiology Data Center and submitted routinely for review to the DSMB.

An additional risk for participants is loss of confidentiality. The risk of breach of confidentiality is best addressed by appropriate study procedures. The PI will be responsible for assuring that study procedures are adhered to regarding data security, transfer, and communications in tracking participants by meeting regularly with study staff, reviewing procedures and performing quality control reviews of study forms.

Data and safety monitoring for continuation, modification, or termination of participation or the clinical trial. The DSMB will review summaries of AEs, SAEs, and Unanticipated Problems and make recommendations for the continuation, modification or termination of the trial. The trial is not expected to have an early termination.

Data Management and Security to Protect Privacy. The University of Pittsburgh Epidemiology Data Center (EDC) has extensive experience with supervising the conduct and data management of clinical trials and will serve as the data coordinating center (DCC) for this study under the direction of [name]. Study data will be maintained on University of Pittsburgh servers. Security and integrity of study resources will be achieved via strictly enforced policies, standards and guidelines which are compliant with federal regulations and guidelines including the Health Insurance Portability and Accountability Act (HIPAA), the Federal Information Security

Management Act of 2002 (FISMA) and Department of Health and Human Services (HHS). Access to the data system requires training and certification with respect to protocol, procedure and security. Access to data on EDC servers is managed by EDC server administrators via Active Directory and Windows Authentication. Study data will be stored on an EDC SQL Server that is behind the University of Pittsburgh enterprise firewall system and is protected in a server VLAN. Direct access to this database server is restricted and is only available to authorized EDC personnel with appropriate credentials and data privileges. Regularly scheduled backups and archives protect central and local information from hard disk failures. Permanent archives of critical project files are created and are stored in a secure off-site facility to prevent data loss due to catastrophic events.

Data collection forms. The EDC will support the research team to develop required protocols, data collection forms and venues for the data collection (e.g., telephone interview, clinic visit). Data collection forms will be designed to ensure protocol compliance, optimize interview flow with branching logic, reduce missing data elements, minimize participant burden in self-reports, and support efficient data collection and analysis processes.

Data Management Manual of Operations. The EDC will assist in developing a Manual of Operations (MOP) to document all data collection and management procedures for the study. The MOP will include an overall description of the project, the study protocol, data collection procedures (including question by question instructions), and detailed descriptions of all other procedures required to conduct the study. In addition, an internal DCC Manual of Operations (DCC MOP) will be developed. The DCC MOP will provide documentation of the internal procedures, such as the creation of analytic data sets, the generation of reports, and the data freeze. The MOPs will facilitate consistency in protocol implementation and provide some protection against potential disruptions due to personnel turnover.

Quality control/Data Collection Monitoring. The DCC will monitor all aspects of study performance and protocol compliance and will be responsible for monitoring the data from all study entities as well as adherence to established adverse event reporting. Electronic data capture methods will be implemented for this study. Study data will be subjected to extensive checks for completeness, accuracy, and consistency including data validations to verify the authenticity of participant IDs, prohibit duplicate record entries, and incorporate range, format, data type checks and alert values. To facilitate monitoring of study performance, data status reports will be generated and reviewed by study leadership on a regular basis. These reports will include recruitment and retention, protocol adherence, data quality, and study participant characteristics. Creation of analytic datasets for statistical programming. The statistical programmer and analyst of the data management team will be responsible for cleaning the datasets and preparing the corresponding codebooks and statistical summaries. These datasets will be used to carry out the full range of data analysis activities needed to prepare monitoring reports, abstracts and manuscripts. This will include planning and developing methods for data analysis, statistical programming, and interpreting and summarizing data for internal and DSMB reports.

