8. STUDY PROCEDURES

8.1 Assessments

Study team will conduct research assessments with each study subject at baseline, and then at 4, 8 and 12 month follow up visits. Sociodemographic, clinical and outcome information will be obtained directly from subjects and through review of their medical records including hospital databases, outpatient records, and insurance records. Study team will administer the assessments as portrayed in table below.

Table 1

Assessment	Screening/	Baseline	4mth Follow-up	8mth Follow-up	12mth Follow-up	Role to assessment
(In order of study procurement)	Consent (in clinic	(in clinic or	(in clinic or	(by phone)	(by phone)	
	or by phone)	by phone)	by phone)			
Clinic Screening Form (includes 6-item screener)	Х					
Consent	Х					
Sociodemographic Characteristics						Exploratory Outcome
Demographics		Х				
Transportation		х				
Kaiser: Your Current Living Situation		x				
Smoking		x				
Alcohol Use		x				
Montreal Cognitive Assessment		Х			Х	
Quality of Life Assessment						Secondary Outcome
AFEQT		Х	Х	Х	Х	
PROMIS-29 Profile v2.0		Х	Х	Х	Х	
Anticoagulant Adherence						Primary Outcome
VOILS: Medication Nonadherence		Х	Х	Х	Х	
VOILS: Medication - Reasons for nonadherence		Х	Х	Х	Х	
Self-Efficacy						Exploratory Outcome
PROMIS Self-Efficacy for Managing Medications & Treatments		Х	Х	Х	х	
PROMIS Self-Efficacy Managing Symptoms		Х	Х	Х	Х	
Social Measures						Exploratory Outcome
BRIEF Health Literacy Screener		Х				. ,
Newest Vital Sign (NSV)		Х				
Connor-Davidson Resilience Scale (CD-RISC-10)			Х			
Berkman-Syme Social Network Index			Х			
Psychiatric Symptoms						Covariate
Patient Health Questionnaire (PHQ-8)		X	Х	Х	Х	
Medical Co-Morbidity Variables						Covariate
AF History		Х				
Vital Signs (BMI)		Х				
Antiarrhythmic Medications		Х	Х	Х	Х	
Other Medications		Х				
Other Medical History		Х				
New AF Therapies (Cardioversion, pacemaker)			X	X	X	
Proportion of Days Covered (PDC)					X	Primary Outcome
Health care utilization (events)			Х	Х	Х	Secondary Outcome
RELATIONAL AGENT/Kardia Information						Exploratory Outcome
Relational Agent usage			Х			
Study team Kardia review time			Х			
AliveCor Tracking			Х			
Satisfaction in using Relational Agent and Kardia			Х			
Cardiac hospitalizations (heart failure myocardial infarction			v	N N		
hospitalization for AF)			X	X	x	
AS NEEDED FORMS:			1			
Adverse Event and Serious Adverse Event monitoring						
Protocol Deviations						
Unanticipated Problems						
Withdrawal						

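### Monitoring and alerts that exist only in the intervention arm feed two of the adverse-event sources, so by-arm counts of non-hospital adverse events may be biased toward more events in that arm.

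*Combined protocol and SAP*

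**What the plan says.** **AE sources.** Section 10.3 gives five: "participant interview at the 4-, 8- and 12-month assessments; direct contact by participants during the scheduled check-in calls"; then "review of the electronic health record; communication from referring physicians" or the participants' own providers; and contact started by family or other surrogates. None is limited to one arm.

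**Contacts common to both arms.** Section 9 states: "All participants will receive scheduled check-in calls at study day 7, 14, 30, 60 and 90". Section 5.0 gives everyone visits at 4, 8 and 12 months. The stated purpose of the calls is support and help with the protocol or devices, and section 10.3 describes AE information from them as "direct contact by participants during the scheduled check-in calls".

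**Monitoring in the intervention arm only.** The dashboard holds agent use, reported symptoms, self-reported adherence, and Kardia rate and rhythm. Section 9 says of it: "Dashboard results will be reviewed daily". Section 7.7 asks for at least one Kardia reading a day and has the principal investigator review the results. Section 4.1 gives controls no Kardia. When results meet set criteria, section 10.1 has the team "send alerts through the electronic health record to the physicians and care teams that provide care for intervention participants". The risk assessment in section 10.3 accepts that device findings may enter the health record and change care.

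**AE form.** Table 1 in section 8.1 places "Adverse Event and Serious Adverse Event monitoring" among the as-needed forms, with no visit marked. The same table marks health care utilization and cardiac hospitalizations at 4, 8 and 12 months.

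**Blinding.** Section 7.6 says that neither participants nor staff are blinded.

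**The concern.** A by-arm AE comparison is fair only if an event of a given kind has about the same chance of being found in either arm. Here health-record review and provider communication have an extra inflow in one arm. The people who record and classify AEs, the project manager and the principal investigator, know the arm, and the principal investigator also reads the Kardia results. The shared contacts could offset this if they carried a fixed AE question, but the documents describe none.

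The Data and Safety Monitoring Board (DSMB) advises on benefit-risk and on continuing, modifying or ending the trial from AE summaries (sections 10.2 and 10.3). With unequal ascertainment, an excess in the intervention arm could be closer watching read as harm, or real harm put down to closer watching. The second matters because section 10.3 names a specific worry: that using the agent may delay participants from seeking care.

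**Working it through.** The plan states no AE rate, detection probability or AE power, so there is no figure to reproduce. The check has two parts.

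**1. Routes by arm**

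| Route (section 10.3) | Open to both arms? | Intervention-only input? |
|---|---|---|
| Interviews at 4, 8, 12 months | Yes | None stated |
| Check-in calls, days 7-90 | Yes | None stated |
| Health-record review | Yes | Yes: alerts and device findings may enter the record |
| Provider communication | Yes | Possible: alerts open an exchange with providers |
| Family or surrogates | Yes | None stated |

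Two of the five routes are fed unequally. The dashboard is not itself a listed AE source, but what it shows reaches the staff who record AEs. Phones are returned at the 4-month visit, so the extra input is concentrated in months 0-4. Hospital events have scheduled enquiry and record review at 4, 8 and 12 months in both arms. What remains exposed is mainly non-hospital AEs.

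**2. Illustration of size**

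From the plan: 132 per arm (section 5.0) and a 4-month device period. Assumed: equal true AE rates of 1 or 2 per person-year, 60% capture in controls, and relative capture in the intervention arm of 1.10, 1.25 or 1.50 during months 0-4 (1.50 × 60% = 90%), equal afterwards.

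- Captured control events by month 4 = 132 × 4/12 × rate × 0.60 = 26.4 (rate 1) or 52.8 (rate 2).
- Intervention count = control count × capture ratio. At 1.50: 39.6 or 79.2.
- Captured control events by month 12 = 132 × rate × 0.60 = 79.2 or 158.4.
- 12-month ratio = (4 × capture ratio + 8)/12 = 1.03, 1.08 or 1.17.

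The chance of a significant excess in the intervention arm, with no true difference, comes from independent Poisson counts and a two-sided 5% conditional binomial test:

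| Capture ratio, months 0-4 | At 4 months (rate 1 / rate 2) | Over 12 months (rate 1 / rate 2) |
|---|---|---|
| 1.00 | 0.018 / 0.020 | 0.021 / 0.022 |
| 1.10 | 0.042 / 0.060 | 0.034 / 0.043 |
| 1.25 | 0.110 / 0.200 | 0.064 / 0.099 |
| 1.50 | 0.326 / 0.603 | 0.152 / 0.278 |

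With a lower rate of 0.42 per person-year (the control utilization rate in section 5.0, Aim 2, used only as a proxy), the 4-month chances are about 3%, 5% and 13%.

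**The case against.** A reader might infer that some AE routes run only in the intervention arm, that otherwise AEs are caught only on an as-needed form, and that this arm is therefore bound to show more events. The documents do not support this. No listed route is arm-restricted. Interviews and calls cover everyone. A form completed when an event occurs is compatible with a scheduled interview; withdrawal and death notification sit in the same list. A true benefit could also offset any surveillance excess. Nor is the whole safety conclusion uninterpretable: hospitalization, the protocol's own example of a serious AE, is sought on the same schedule in both arms.

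Three further points have force.

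- The mechanism is partly inferred. Alerts travel from the team to the provider, and nothing says that providers report back or that a symptom entry or AF reading is logged as an AE.
- The plan contains no between-arm AE significance test, AEs are also judged case by case for relatedness, and independent Poisson counts ignore repeat events within a person. The probabilities gauge how misleading a count could be; they are not error rates of a planned analysis.
- AE templates and case report forms are assigned to the DSMB charter, and data collection instructions to the Manual of Operations. A script or source field may exist there, though these documents do not say so.

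What stands is that one arm is watched more closely, by unblinded staff, through inputs that reach two AE sources, with no stated rule to equalize the enquiry or identify how an event was found.

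**Conclusion.** The concern holds in limited form. By-arm AE counts may be biased toward more events in the intervention arm, mainly for non-hospital AEs in months 0-4. The direction is likely; the size cannot be known from the documents. Under the assumptions above, the chance of a nominally significant false excess is about 4-6%, 11-20% or 33-60% at 4 months for capture 10%, 25% or 50% higher, and about 3-4%, 6-10% or 15-28% over 12 months. Equal capture gives about 2%. The result depends wholly on the assumed capture gap and AE rate. The change is worth making because it is cheap and the DSMB relies on these counts.

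**What to change.** 1. In Table 1, mark the same scripted AE query for both arms at the day 7, 14, 30, 60 and 90 calls and at the 4-, 8- and 12-month assessments.
2. On the AE form that the data center is to develop, record every source through which the event was known, and whether a dashboard reading or alert preceded it. A first-source field alone would not show which events were known only from the dashboard or an alert.
3. Keep the all-events by-arm table of AEs and serious AEs as the main safety table for the DSMB and the final report. Add a second by-arm table limited to events also found through the scheduled contacts common to both arms, with events known only from the health record after an alert shown separately. The second table must not replace the first: alerts are part of the intervention under test, and dropping events found that way could hide real harm.

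Individual reporting to the IRB, NHLBI and DSMB is unchanged. The cost is one scripted question at existing contacts, one extra form field and one extra table.
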